### 1.0 Primary endpoint:

Time from randomization to date of progression or residual disease of previously treated lesions as determined by the date of the radiologic imaging.

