## **D. RESEARCH DESIGN AND METHODS**

### **1.0 Eligibility**

#### **1.1 Inclusion Criteria**

- Subjects with HCC are eligible for this trial. HCC is defined as having at least one of the following:
  - Biopsy proven HCC or:
  - A discrete hepatic tumor(s) as defined by the Barcelona (29) criteria for cirrhotic subjects,  $\geq$  2cm with arterial hypervascularity and venous or delayed phase washout on CT or MRI.
- Subjects are liver transplant candidates (actively awaiting organ transplant per transplant services in documentation), or, potential liver transplant candidates (at the discretion of the liver team and/or Principal Investigator) advised by liver transplant services as needing local treatment prior to liver transplant evaluation.
- Subjects must be within UCSF criteria (one solitary tumor smaller than 6.5 cm, or patients having 3 or fewer nodules, with the largest lesion being smaller than 4.5 cm or having a total tumor diameter less than 8.5 cm without vascular invasion) and eligible for potential liver transplant.
- Subjects must be eligible for standard TACE and SBRT procedures.
- Subjects must have a life expectancy of at least 12 weeks.
- Subjects must be 18 years of age or older. Adult subjects of all ages, both sexes and all races will be included in this study.
- Subjects must sign an informed consent form approved for this purpose by the Institutional Review Board (IRB) of record.
- Subjects must have a Child-Turcotte-Pugh (CTP) score  $\leq 8$ .
- Patients must have adequate organ function within 2 weeks of enrollment.
  - Bone marrow: Platelets  $\geq 30,000/\text{mm}^3$
  - Renal: BUN  $\leq 40 \text{ mg/dl}$ ; creatinine  $\leq 2.0 \text{ mg/dl}$
  - Hepatic: INR  $\leq 1.5$  or correctable by Vitamin K, unless anti-coagulated for another medical reason
  - Bilirubin  $< 3.0 \text{ mg/dl}$  (in the absence of obstruction or pre-existing disease of the biliary tract, e.g. primary sclerosing cholangitis).
- Patients' uninvolved liver volume will be estimated and must be  $> 700\text{ml}$ .
- Patients must have a Zubrod performance status of  $\leq 2$ .
- Patients who are sexually active must agree to the use of contraception throughout the duration of the study.

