## 3.0 Randomization Plan

All consented subjects will receive a Study Identification Number (SID) in the EDC system. The SID number will be a 4 digit number. The first two digits are site number. Site number will be assigned by the Coordinating Center at Lahey and it will start with 01 with 1 increment for each site (that is 01, 02, 03, etc.). The last two digits are the patient screening order starting from 01. Eligible subjects will be randomized after eligibility is confirmed by the provider, as soon as practical to the baseline tumor scan. Randomization will be performed using randomly selected block sizes of 2, 4 and 6 and stratified by the

following factors identified at screening: CTP score (either A or B) and disease etiology (with or without Hepatitis C). The randomization ID will be a 5 digit number in the form of ABCDE where, AB denote the site number, C indexes the four strata used for the randomization and DE index the order of screening at that site. C will be one of the numbers from 1 to 4. DE is the patient screening order starting from 01. Each study site will receive randomization list from the Coordinating Center at Lahey and randomize the eligible subjects individually. Site staff involved in randomizing subjects will not be aware of the randomization sequence before randomization. Randomization will be documented on both source document and EDC indicating assignment. If a patient is lost from the study because they are unable to receive their randomized treatment then an additional patient will be enrolled.(i.e., unable to meet SBRT dose constraints or achieve an acceptable respiratory motion strategy for SBRT). Individual randomization codes will be not be reused.

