4.3.2 Energy: Treatment will be delivered with 6 - 18 MV photons

4.3.3 Localization, simulation, and immobilization: All subjects must undergo CT simulation prior to treatment. A patient will be simulated using an immobilization device that allows for reproducible treatment setup using an Alpha Cradle, Vac-Lok, or other commercially available SBRT immobilization system. Patients will be simulated supine with both arms up if tolerated. IV and oral contrast will be used at the discretion of the treating radiation oncologist. CT images should be obtained from at least 2cm above the dome of the diaphragm to the bottom of the kidneys. 1-2mm cuts should be performed for high resolution delineation of the tumor and surrounding structures.

A motion management strategy is strongly encouraged to minimize liver motion. Acceptable motion management strategies include active breathing control (ABC) or similar breath hold device, respiratory gating, tumor tracking using Cyberknife synchrony system, or abdominal compression using an abdominal belt or paddle. Patients who cannot be treated using one of these techniques may be treated free breathing with a tumor-specific internal target volume (ITV) if tumor motion is  $\leq 10$  mm in maximal extent in any one direction and treatment planning dose constraints can be met. 4DCT scan is required when a tumor-specific internal target volume (ITV) is being used.

Prior to each SBRT treatment, the liver will be imaged. For patients with fiducial markers within the liver, the tumor may be localized using fluoroscopy, orthogonal kV images, or cone-beam CT scans using the fiducials as surrogate markers for the liver tumor. For patients without fiducial markers, cone-beam CT or other types of volumetric image guided radiation therapy (IGRT) available (e.g.

MR guidance) will be used to image the tumor and/or portion of the liver where the tumor lies as and soft tissue surrogates for the tumor for positioning prior to treatment.

Documentation of CT-based simulation including setup, use of IV contrast, type of motion management, and image-guidance used for treatment delivered is required.

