##### 4.4.2 Critical Normal Tissue Constraints

###### Mandatory dose constraints:

Liver minus GTV's: volume >700cc

Liver minus GTV's: Mean <18 Gy

Spinal Cord: max dose to 0.5cc is 25Gy

Stomach: max dose to 0.5cc 30Gy

Duodenum: max dose to 0.5cc is 30Gy

Small Bowel: max dose to 0.5cc is 30Gy

Large Bowel: max dose to 0.5cc is 32Gy

Esophagus: max dose to 0.5cc is 32Gy

Kidneys bilateral mean dose <10Gy, or if there is only one kidney V10Gy<10% (or constraint for contralateral kidney, if mean dose is >10Gy to combined both kidneys)

Heart max 0.5cc <105% PTV prescription dose

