#### 13.1 Primary Variable

Time to residual/recurrent disease is defined as the time from the date of randomization until the date of residual/recurrent disease within the treated lesion(s). Any subject not known to have had residual/recurrent disease before transplant will be censored based on the last recorded date on which the

subject was still on study. The percentage of subjects who had residual/recurrent disease will also be derived.

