### 17.1 Primary endpoint

The primary analysis of the primary endpoint of time from randomization to residual or recurrent disease will be based upon the Kaplan-Meier estimates of time to event for the two groups where the two groups are compared using the log-rank test. Patients will be censored at time of transplantation or two years, whichever comes first. The primary analysis will treat patient death as residual or recurrent disease (effectively the compound endpoint of residual or recurrent disease or death). During the time frame of two years mortality should be low, but treatment of death as residual or recurrent disease is conservative. Secondary analyses using the Cox regression model will explore predictors of recurrence beyond group assignment, and also explore interactions between treatment and these other factors. We will also explore sex and treatment center differences. Secondary analyses will also censor for deaths unrelated to treatment. Statistical tests will be made at the two-sided 5% level.

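### Randomised patients who cannot receive their assigned treatment may be lost and replaced, mainly from the SBRT arm, and no as-randomised analysis set is named, so the primary comparison could be biased in an unknown direction

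*Combined protocol and SAP*

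**What the plan says.** Section 3.0 (Randomization Plan) provides: "If a patient is lost from the study because they are unable to receive their randomized treatment then an additional patient will be enrolled". The reasons that follow are being "unable to meet SBRT dose constraints or achieve an acceptable respiratory motion strategy for SBRT". The same section says that individual randomisation codes are not reused.

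Section B.1.0 defines the primary endpoint as "Time from randomization to date of progression or residual disease of previously treated lesions as determined by the date of the radiologic imaging". Section 13.1 likewise places the event within the treated lesion(s), and adds: "Any subject not known to have had residual/recurrent disease before transplant will be censored based on the last recorded date on which the" subject remained on study.

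Section 17.1 compares two groups by Kaplan-Meier and log-rank, censoring at transplantation or two years, without saying who belongs to the groups. Its nearest hint is that secondary Cox analyses "will explore predictors of recurrence beyond group assignment".

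Section 12.2 takes patients off study if they decompensate before initial therapy. It does not mention planning failure.

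**The concern.** Planning failure for SBRT is discovered by trying to plan SBRT, so under section 3.0 it removes patients chiefly from one arm, in a trial that section 15.0 describes as non-blinded. Patients in the TACE arm who would also have failed SBRT planning are never identified and stay in. Extra enrolment restores the number of patients but not the balance that randomisation gave.

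The endpoint definition compounds this. A patient who was never treated has no treated lesion in which an event can be recorded. Under section 13.1 the most such a patient could contribute is a few days of follow-up before censoring, and that censoring may be related to prognosis. If those lost would have done worse than average, the comparison leans towards SBRT; if better, towards TACE; at equal prognosis there is no bias.

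**Working it through.** **1. The plan's own figure.** Section 16.0 and Table 7 give HR 0.6, two-sided 5%, 80% power, 120 events and 98 per arm. Schoenfeld's formula gives 4 × (1.960 + 0.842)² / (ln 0.6)² = 4 × 7.849 / 0.2609 = 120.3, which agrees. The TACE median is 134 days, and 134 / 0.6 = 223 days for SBRT, as in Table 7.

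**2. Why one-sided loss matters.** Suppose there is no true effect and 10% of patients cannot be planned for SBRT. They leave the SBRT arm and stay in the TACE arm. With plannable hazard h:
- Unplannable hazard 2h: TACE starts at 0.9h + 0.1 × 2h = 1.10h, so the apparent initial HR is 1/1.10 = 0.91.
- Unplannable hazard 0.5h: TACE starts at 0.9h + 0.1 × 0.5h = 0.95h, so the apparent initial HR is 1/0.95 = 1.05.

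Over follow-up, a simulation with 98 per arm and 3,000 trials per setting gave average HRs of about 0.94 and 1.08. Censoring these patients at about day 14 instead of excluding them gave 0.96 and 1.08, so reading section 13.1 as keeping them in the dataset does not remove the problem.

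**3. Error rate under the rule as written.** From the documents: TACE median 134 days, 15% yearly dropout, 365-day accrual, two-year study. Scans every three months are modelled as a 91-day grid. Assumed: the share lost, its hazard ratio to other patients, exponential times, and transplant censoring of either none or 50% by two years (section 16.0 says only that more than 50% is believed). With replacement, randomised numbers per arm are 98 / 0.975 = 101 at 5% lost and 98 / 0.95 = 103 at 10% lost. Log-rank test at two-sided 5%, 40,000 trials per setting, no true effect. Ranges are across the two transplant assumptions:

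| Lost from SBRT | Hazard of those lost | SBRT wins | TACE wins | Two-sided |
|---|---|---|---|---|
| 5% | 2× | 3.7% | 1.6-1.7% | 5.3-5.4% |
| 10% | 2× | 5.4% | 1.1-1.2% | 6.5% |
| 10% | 0.5× | 0.8-1.0% | 6.1-6.9% | 7.0-7.7% |
| 10% | 1× | – | – | 4.9-5.1% |

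Nominal is 2.5% on each side. Across 2% to 5% lost at twice or half the hazard, with transplant censoring, a further run of 10,000 trials per setting gave 5.3% to 5.8% two-sided. Weekly instead of 91-day detection left the setting with 10% lost and twice the hazard at 6.4% to 6.5%, so the scan grid is not the cause.

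**4. Keeping everyone as randomised.** Two scoring rules were tried for unplannable SBRT patients. Rule A follows them under whatever therapy they receive, with event times like those of similar TACE patients. Rule B counts their untreated lesions as events at the first scan. Power at HR 0.6 in plannable patients, 10% failure and twice the hazard (20,000 trials; lower figure 98 per arm, upper 103):

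| Transplant censoring | No failures | Rule A | Rule B |
|---|---|---|---|
| 50% by two years | 81% | 72-74% | 62-65% |
| None | 88% | 81-82% | 73-76% |

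With no true effect, rule A gives 5.1% to 5.2% two-sided error at 10% failure and twice the hazard. Rule B gives TACE wins of 4.5% to 4.9% at twice the hazard and 8.7% to 8.9% at equal prognosis. That excess may be a real consequence of being assigned a treatment that cannot be given, rather than bias.

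**The case against.** Several passages limit the problem, and most of what they say stands.

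- **Follow-up may already cover these patients.** Table 4 visits run from randomisation. Section 11.1.3.4 images listed patients at 90-day intervals and unlisted patients until the primary endpoint is met. Neither expressly requires treatment. But section 3.0 describes these patients as lost, and Table 4 is headed as follow-up after the initial treatment phase. The text is ambiguous, not empty.
- **Failures may be few.** Section 1.1 requires eligibility for both procedures, and "Patients' uninvolved liver volume will be estimated and must be" above 700 ml, which matches the first mandatory SBRT constraint ("Liver minus GTV's: volume >700cc"). The prescription dose can vary (section 4.4.3.3). On motion, "Patients who cannot be treated using one of these techniques may be treated free breathing" within stated limits. These reduce losses, yet section 3.0 still expects some.
- **Some failures may surface before randomisation.** Simulation is listed in the screening column of the Arm A calendar (Table 2). That column also contains randomisation, so the order is unclear, and the TACE calendar (Table 3) has no simulation.
- **Section 3.0 is an enrolment rule.** It does not say that lost patients are left out of the analysis. A reader might infer an express exclusion; the documents do not support that. The difficulty is that nothing states the opposite.
- **The question asked is about treated lesions.** The synopsis objective says so, and assessing target lesions in untreated patients widens it. That is why the extension should be confined to these patients and the treated-only comparison retained as a sensitivity analysis.

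**Conclusion.** The point holds as a gap that should be fixed: a replacement rule whose stated reasons all arise in one arm, an endpoint tied to treated lesions, and no named as-randomised set. A reader might infer that the rule favours SBRT. The documents do not support that, since they give no prognosis for patients who fail planning, and the illustration moves either way.

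The size rests wholly on assumptions. A 10% loss from SBRT alone at twice or half the hazard takes the two-sided error to about 6.5% to 7.7%, concentrated on one side. At 5% lost or fewer it stays close to nominal, and at equal prognosis there is no bias. Removal for decompensation under section 12.2 can affect both arms and was not modelled.

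**What to change.** 1. State in section 17.1 that the primary analysis includes every randomised patient in the assigned arm.
2. Amend section 3.0 so that patients not treated as assigned stay on the existing imaging schedule (Table 4 and section 11.1.3.4) and are not dropped.
3. For these patients, assess the target lesions identified at randomisation, with a scoring rule fixed before any outcome comparison.
4. Report non-treatment by arm and reason.
5. Make the treated-only comparison a sensitivity analysis.

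Replacement can continue as additional enrolment; the bar on reusing codes already fits this.

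The cost is protocol and SAP wording, plus recording scans for what may be few patients, many of whom would be scanned anyway. The real price is dilution of the SBRT effect. Rule B costs considerably more power than rule A, so the scoring rule should be chosen with the power table above in view, and the 80% stated in section 16.0 qualified accordingly.

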## **4.0 Treatment Plan for SBRT**

4.1 Once randomized, subjects will be consented per the site's standard for SBRT or TACE prior to starting treatment.

### **4.2 Placement of Fiducial Markers**

Fiducial markers are highly encouraged but not mandatory. This will be decided by the treating radiation oncologist based on clinical information and treatment delivery capabilities. If used, fiducials will be placed percutaneously within the liver in close proximity of the target tumor. At least 3 fiducial markers are recommended when used.

### **4.3 Stereotactic Body Radiotherapy**

4.3.1 Conformal treatment planning will be used for all subjects, based on a simulation CT scan. Either 3D Conformal Radiation Therapy, Intensity Modulated Radiation Therapy, or Arc Rotational Therapy may be used as appropriate.

4.3.2 Energy: Treatment will be delivered with 6 - 18 MV photons

4.3.3 Localization, simulation, and immobilization: All subjects must undergo CT simulation prior to treatment. A patient will be simulated using an immobilization device that allows for reproducible treatment setup using an Alpha Cradle, Vac-Lok, or other commercially available SBRT immobilization system. Patients will be simulated supine with both arms up if tolerated. IV and oral contrast will be used at the discretion of the treating radiation oncologist. CT images should be obtained from at least 2cm above the dome of the diaphragm to the bottom of the kidneys. 1-2mm cuts should be performed for high resolution delineation of the tumor and surrounding structures.

A motion management strategy is strongly encouraged to minimize liver motion. Acceptable motion management strategies include active breathing control (ABC) or similar breath hold device, respiratory gating, tumor tracking using Cyberknife synchrony system, or abdominal compression using an abdominal belt or paddle. Patients who cannot be treated using one of these techniques may be treated free breathing with a tumor-specific internal target volume (ITV) if tumor motion is  $\leq 10$  mm in maximal extent in any one direction and treatment planning dose constraints can be met. 4DCT scan is required when a tumor-specific internal target volume (ITV) is being used.

Prior to each SBRT treatment, the liver will be imaged. For patients with fiducial markers within the liver, the tumor may be localized using fluoroscopy, orthogonal kV images, or cone-beam CT scans using the fiducials as surrogate markers for the liver tumor. For patients without fiducial markers, cone-beam CT or other types of volumetric image guided radiation therapy (IGRT) available (e.g.

MR guidance) will be used to image the tumor and/or portion of the liver where the tumor lies as and soft tissue surrogates for the tumor for positioning prior to treatment.

Documentation of CT-based simulation including setup, use of IV contrast, type of motion management, and image-guidance used for treatment delivered is required.

**4.3.4 Radiation target volumes:** The gross tumor volume (GTV) will be defined using the planning CT scan with the aid of a diagnostic imaging (contrast-enhanced CT or MRI). GTV is defined as all parenchymal HCC. No clinical target volume (CTV) will be used in this study. The PTV expansion will be determined based upon the immobilization device(s) used. Minimum PTV margin will be 0.5 cm circumferentially.

#### 4.4 SBRT Planning Guidelines - Radiation Doses:

##### 4.4.1 PTV Target Doses

**4.4.1.1** The highest allowable doses to the target volumes that maintain normal tissue constraints should be used. The prescription isodose surface covers at least 95% of PTV. A goal is that 100% of the GTV is encompassed by the prescription dose. Prescription dose should not extend beyond the PTV.

##### 4.4.1.2 Variations

- Minor variation is defined as minimum PTV dose falling between 85% and 94.9% of the prescription isodose line
- Major variation (unacceptable) is defined as minimum PTV dose < 85% of the prescription isodose line.

**4.4.1.3** Maximum doses are defined at 1 cc of volume. Maximum dose should be within the PTV <150% of the prescribed dose.

##### 4.4.2 Critical Normal Tissue Constraints

###### Mandatory dose constraints:

Liver minus GTV's: volume >700cc

Liver minus GTV's: Mean <18 Gy

Spinal Cord: max dose to 0.5cc is 25Gy

Stomach: max dose to 0.5cc 30Gy

Duodenum: max dose to 0.5cc is 30Gy

Small Bowel: max dose to 0.5cc is 30Gy

Large Bowel: max dose to 0.5cc is 32Gy

Esophagus: max dose to 0.5cc is 32Gy

Kidneys bilateral mean dose <10Gy, or if there is only one kidney V10Gy<10% (or constraint for contralateral kidney, if mean dose is >10Gy to combined both kidneys)

Heart max 0.5cc <105% PTV prescription dose

###### Optional Dose Constraint:

Liver minus GTV's: V10Gy <70%

Common bile duct: max dose to 0.5cc <50Gy

Skin external: max 0.5cc<32 Gy

##### 4.4.3 Radiation Schedule

**4.4.3.1** SBRT will be delivered in five total fractions. The entire treatment must be delivered within 15 total days.

4.4.3.2 Three dimensional treatment planning will be used for all subjects. Volumes of tumor and normal liver will be determined, and DVH based treatment planning will be carried out, targeted to the tumor only.

4.4.3.3 Radiation Prescription Dose: The goal is to use the highest allowable prescription dose to the primary target while respecting normal tissue constraints. Dose prescription is based on the volume of normal tissues irradiated (correlated with mean liver dose) as well as proximity of stomach, duodenum, small and large bowel (GI luminal structures) to the target volumes. In the absence of adjacent GI luminal structures that may limit dose, the PTV dose prescription should be based on mean liver dose (MLD is the mean dose to the liver minus GTV's). See table below.

The dose to multiple PTVs within the same subject may vary. Conformality of the prescription dose and the 30Gy isodose lines are planning goals.

For CTP A: 27.5 Gy - 50 Gy in 5 fractions

For CTP B: 27.5 Gy - 40 Gy in 5 fractions.

**Table 1: Priority Constraint - Mean Liver Dose (Gy) [liver-GTV's]**

GTV	Prescription Dose If max MLD exceeded
<15.0	50 Gy
15.0	40 Gy
15.5	35 Gy
16.0	30 Gy
17.0	27.5 Gy

## **5.0 Treatment Plan for TACE**

Subjects will be consented to TACE with Quadrasphere® Microspheres either with or without doxorubicin as per standard of care at the treating institution.

